15.4 Safety Analyses

The ITT data set (all randomized subjects) will be considered evaluable for safety. Skin irritation scores will be reported for any subject who is scored with a 1 or more at any observation [baseline (screening day and treatment day), post-application/prior to 10-minute, and 6-hours sampling procedures], in any category for any site.

Adverse Events (including post treatment skin irritation scores of 3), will also be summarized. Summary tables will present incidence rates of adverse events by treatment group for all subjects who enter the treatment period. Listings of Adverse Events will be provided.

The statistical significance of differences in skin irritation between the Investigational Product, Active Control and Vehicle Control will be evaluated using Fisher's exact test on skin irritation data summarized as follows: any reaction above zero (no reaction) on the skin irritation rating scale for any category (erythema, edema, rash, and dryness) will be considered a positive signal for that substance. If Fisher's exact test shows statistically significant skin irritation between the two active treatments and Vehicle Control a secondary analysis will be conducted to determine how the reactions differ.

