7.5 Safety Analysis

The full Intent to Treat data set (all randomized subjects) will be used for the safety analysis. The principal measures of safety will be skin irritation scores and the incidence of adverse events reported during the study.

Differences between the Investigational Product, Vehicle Control, and Active Control will be evaluated on skin irritation data.

7.6 **Study Flow Chart**

Procedure	Timeline (Days)			
	14 or more	2 on more prior	0	Treatment Day
	prior to Baseline	3 or more prior to Baseline	0 Baseline	3 or more post Baseline
Informed Consent Obtained	X			
Product-Restriction Period	X	X	X	
Inclusion/Exclusion Criteria including Medical History Reviewed	X	X	X	X
Clipping Hair From Test sites		X		
Baseline Screening			X	
Test-Day Baseline Sample		= 0,		X
Product Application				X
10-Minute Post-Product Application Sample				X
6-Hour Post-Product Application Sample				X
Adverse Events		X	X	X

Note: Visual evaluations of the skin on each test area will be performed at each laboratory visit prior to treatment, and prior to 10-minute and 6-hour post-treatment microbial sampling.

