13.3 Randomization

Subjects will be randomized to treatment using the following block design:

Treatment Balance

Each subject will receive two different treatments, one on the right side of the body and one on the left. This means there are three possible combinations of treatments (assuming A and B are either Investigational Product or Active Control; C is Vehicle Control):

- A and B
- A and C
- B and C

The treatment assignments will be balanced such that the number of readings per anatomical site matches the calculated requirements. The Investigational Product and Active Control will be applied to an equal number of anatomical sites. The Vehicle Control will be compared against each active substance an equal number of times. The Vehicle Control will be applied to the number of anatomical sites necessary to generate a baseline for comparison to the active substances.

A minimum of 56 evaluable subjects will be required to achieve a total of at least 112 test sites for groin and abdominal regions. Out of the minimum 56 evaluable subjects, 40 evaluable subjects will receive treatments from both A and B, 8 evaluable subjects will receive treatments from both A and C and 8 evaluable subjects will receive treatments from both B and C to achieve 48 evaluable test sites from Investigational Product and Active Control arms (A and B) and 16 evaluable test sites from Vehicle Control arm (C) for groin and abdominal regions.

Left/Right Balance

The application will be randomized so that each treatment is used on an equal number of left and right sides of the body.

Site and Sample Time Balance

Each groin and abdomen sample site is divided into four areas and three of the areas will be sampled – one at baseline, one at 10 minutes, and one at 6 hours. The remaining area will not be used. Therefore, for any groin or abdomen site there are 24 possible sampling orders.

The number of subjects required for a completely balanced block design for all factors at once is dependent on the ratio of the number of anatomical sites used in the active treatments compared to the number of anatomical sites used in the Vehicle Control treatment but is in any case a multiple of 48 (a factor of two for left/right balance times a factor of 24 for sample order balance). The exact subject numbers and Active/Vehicle Control ratio may make it infeasible to provide a completely balanced block design, so the following priority order will be used for design:

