7.0 CALCULATIONS AND DATA HANDLING

Count colonies on plates that have between 25 and 250 colonies per plate. If no plates provide counts in that range, counts from those plates closest to that range will be used for analysis.

The microbial population recovered from each replicate of Test A, Test B, Test C, and Test D will be calculated as follows:

 Log_{10} Average Population = $log_{10}(C_i \times 10^{-D})$

Where:

 C_{i} Average of the plates counted

D Dilution Factor of the plates counted (for example, the dilution =factor is 0 for plating 1.0 mL aliquots and is -1 when plating 0.1

mL aliquots.)

NOTE: The reason that a log₁₀ transformation will be performed on the collected data is to obtain a linear scale. A linear scale, more appropriately a log₁₀ linear scale, is a basic requirement of the statistical models used in this study.

If colonies on one of the plates are uncountable, the count from the remaining plate will be used.

The raw data from sampling of all sites evaluated on a subject will be recorded on data collection forms.

8.0 **STATISTICS**

After calculating the log₁₀ populations recovered from Tests D, B, and A, these will be statistically compared to the Initial Population (Control) using a One-Way Analysis of Variance (ANOVA) with Dunnett Multiple Comparisons with the Control. All statistical calculations will be performed using the 0.05 level of significance for Type I (α) error.

Prior to comparing Phases to the Initial Population (Control), the 30-minute evaluation of the Initial Population should be shown to be statistically equivalent to the "time-zero" Initial Population of the microorganism. Hypotheses are:

 H_0 : Initial Population = Test Phase, or

 H_A : Initial Population \neq Test Phase.

If $p \le 0.05$ for each comparison to the control, H_0 will be rejected and the Test Phase will be considered to be significantly different from the Initial Population. There is potential for low variance of the data, which would result in rejecting H_0 . The difference between the Initial Population and the Test Phase will also be used to confirm significant differences. If the difference is greater than or equal to 0.20, the two tests will be determined to be significantly different. Differences less than 0.20 between the two tests will be determined to be not different.

The Product Efficacy Evaluation is effective if the antimicrobial test product produces a significant reduction in the population of the microorganism.

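### Section 15.4 compares skin irritation between products by a Fisher p-value alone; it should add the rate difference and its 95% confidence interval

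*Combined protocol and SAP*

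**What the plan says.** Section 7.5 gives irritation its status: "The principal measures of safety will be skin irritation scores and the incidence of adverse events reported during the study". It adds that differences among the three products will be evaluated on these data.

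Section 15.4 says how. The endpoint is binary: "any reaction above zero (no reaction) on the skin irritation rating scale for any category" counts as a positive signal for the product concerned. Then: "The statistical significance of differences in skin irritation between the Investigational Product, Active Control and Vehicle Control will be evaluated using Fisher's exact test". A secondary analysis of how the reactions differ is conditional on a significant result. The section does not state the significance level, whether the test is one- or two-sided, whether it is pairwise or across three groups, or whether the unit is a site, a region or a subject. The only explicit level for a test is in Appendix 3, Section 8.0, where the neutralization statistics are "performed using the 0.05 level of significance for Type I" error.

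Section 13.3 fixes the numbers: "40 evaluable subjects will receive treatments from both A and B", and "8 evaluable subjects will receive treatments from both A and C and 8 evaluable subjects will receive treatments from both B and C", where A and B are the two active products and C is Vehicle. The Vehicle total is "16 evaluable test sites from Vehicle Control arm (C) for groin and abdominal regions".

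On precision elsewhere, Section 15.1 plans 95% intervals for each product's responder rate, and Section 15.2 plans intervals for differences in log reduction.

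**The concern.** A p-value from a small comparison does not show how large an excess in irritation the data still allow. If the test against Vehicle is not significant, the planned comparison stops there, with no estimate and no bound. The adverse event tables do not fill the gap. Section 14.2 says scores of 1 and 2 are expected after the procedures and are not adverse events, so those tables leave out everything below a score of 3. Section 7.4 says the study is to inform Phase 3, and for that purpose the size of any excess, with its upper limit, is what the next team needs.

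**Working it through.** **Inputs from the protocol.** Sites per region from Section 13.3: Investigational Product (IP) 40 + 8 = 48; Active Control 40 + 8 = 48; Vehicle 8 + 8 = 16. The total is 48 + 48 + 16 = 112 = 2 × 56, which agrees with the stated minimum.

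**Assumptions, because the protocol gives no figure.** Two-sided 0.05; independent sites; Vehicle irritation rate from 0% to 80%, with the comparison product 20 points higher.

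**Formula.** Power = Σₐ Σ_b Bin(a; n₁, p₁) · Bin(b; n₂, p₂) · 1{Fisher p(a, b) ≤ 0.05}, summed over all possible outcomes. Missed = 1 − power.

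**IP (or Active Control) v Vehicle, one region, 48 v 16, 20-point excess:**

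| Vehicle rate | Power | Missed |
|---|---|---|
| 0% | 24.1% | 75.9% |
| 5% | 29.1% | 70.9% |
| 10% | 28.6% | 71.4% |
| 20% | 27.0% | 73.0% |
| 30% | 27.1% | 72.9% |
| 50% | 24.2% | 75.8% |
| 60% | 28.4% | 71.6% |
| 70% | 41% | 59% |
| 80% | 65% | 35% |

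A 30-point excess (40% v 10%) is missed 38% of the time. At Vehicle rates of 5% to 30%, it takes a 40-point excess to reach about 78% to 92% power.

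**Other readings of the same sentence, 20-point excess:**

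- One-sided 0.05, 48 v 16: missed 50% to 71% for Vehicle rates of 0% to 60%.
- Regions pooled, 96 v 32, two-sided: 30% v 10% missed 38%; 50% v 30% missed 52%.
- IP v Active Control, 48 v 48, two-sided: 30% v 10% missed 39%; across Active Control rates of 5% to 60%, missed 28% to 57%.
- One three-group test, 48/48/16, Vehicle rates of 5% to 40%: missed 24% to 55% if only IP is raised, 68% to 77% if both active products are raised.
- More Vehicle sites than the minimum, for example 60 v 20 (an assumption): 30% v 10% missed 60%; 50% v 30% missed 69%.

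**What an interval would show.** Take 14/48 v 1/16, that is 29.2% v 6.3%. Fisher's p = 0.089, not significant. The difference is 22.9 points. The Wilson limits are 18.2% to 43.2% and 1.1% to 28.3%, so the Newcombe limits are:

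- lower: 22.9 − √(10.9² + 22.1²) = 22.9 − 24.6 = −1.7 points
- upper: 22.9 + √(14.0² + 5.1²) = 22.9 + 14.9 = +37.8 points

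A result far from significance is also wide: 10/48 v 3/16 gives p = 1.00, a difference of +2.1 points and limits of −23.8 to +20.2. Both p-values are compatible with an excess of 20 points, and only the interval shows it.

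**The case against.** Several points on the other side stand.

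- A reader might infer that a non-significant test will be reported as no difference from Vehicle. The protocol does not say so. It says only that further analysis depends on significance.
- A reader might apply a miss rate of about 70% to every comparison between products. It belongs to comparisons with Vehicle at 48 v 16, two-sided 0.05 and Vehicle rates up to about 60%. Section 14.2 expects scores of 1 or 2 after the procedures, so a higher Vehicle rate, with a lower miss rate, cannot be excluded.
- Sixteen is a minimum of evaluable sites. Safety uses all randomized subjects, so the Vehicle count may be larger.
- A reader might infer that safety is held to a lower standard than efficacy throughout. That is only partly so. The intervals in Section 15.1 are for single products, and Section 15.2 names only a two-proportion test for differences in responder rate. Only differences in log reduction have a planned interval.
- Low power is not in itself an error. Sections 7.4 and 15.1 say the study is not powered to show efficacy. No such statement covers irritation, but this point does not ask for more subjects.
- Section 15.4 reports the scores of 1 or more, so rates could be derived afterwards. Section 15.0 defers detail to a separate analysis plan, which is not in the text available and might already supply the estimate.

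None of this puts an irritation rate difference or an interval into the protocol, and Section 15.1 itself deals with limited precision by planning intervals and warning that they may not lie entirely above 70%.

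**Conclusion.** The point holds as an inexpensive improvement to a stated method. In this protocol the only stated between-product result for a principal safety measure is whether Fisher's test is significant. At the minimum 48 v 16 sites in one region, a 20-point excess over Vehicle is missed about 71% to 76% of the time. That figure rests on independent sites, two-sided 0.05 and Vehicle rates of 0% to 60%, none of which Section 15.4 states. The miss rate falls to 59% and 35% at Vehicle rates of 70% and 80%, and it is lower with regions pooled, between the two active products, or with more Vehicle sites. The conclusion that survives all these readings is narrower: a non-significant p-value does not bound the excess, and the plan provides nothing that does. The documents do not support the stronger claim that the sponsor will read non-significance as equal irritation.

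**What to change.** In Section 15.4, and in the separate analysis plan, make estimation the main comparison. For IP minus Vehicle, Active Control minus Vehicle and IP minus Active Control, report by region the difference in the proportion of sites with any reaction and its 95% confidence interval. Use a method that allows for two products on the same subject, for example a risk-difference model by generalised estimating equations with the subject as cluster; Newcombe's interval is a simple fallback. Keep Fisher's test as a supporting p-value, and state its level, sidedness, form and unit of analysis. A sentence saying that a non-significant test will not be reported as absence of a difference would be a useful but optional addition.

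The cost is wording and a few extra table columns, with no change to design, subjects or procedures. The downside is that intervals against Vehicle will be wide, which makes the safety statement more cautious.

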14.0 ASSESSMENT OF SAFETY

14.1 **Safety Assessments**

The subject's safety will be monitored by evaluations of reactions observed on the skin of the test sites and any adverse reactions. Adverse reactions will be documented per BSLI Standard Operating Procedure, reported as an Adverse Event, and followed to resolution.

14.2 **Evaluation of Test Sites**

Prior to product application and before any subsequent samples, test site erythema, edema, rash, and dryness will be rated on a 4-step scale, the Skin Irritation Scoring System (Draize). If a subject receives a score of 1 for erythema, edema, rash, and/or dryness prior to Screening Baseline Day or product application on Treatment Day, they will be dismissed from testing. If a subject receives a score of 3 for erythema, edema, rash, and/or dryness at any point in the study, they will be dismissed from testing and reported as an adverse event. (Note: Skin irritation scores of 1 or 2 are expected after sampling and product application procedures and are not grounds for dismissal and will not be considered adverse events.)

SKIN IRRITATION SCORING SYSTEM (Draize)

	0	No reaction
E 41	1	Mild and/or transient redness limited to sensitive area
Erythema	2	Moderate redness persisting over much of the product-exposed area
	3 *	Severe redness extending over most or all of the product-exposed area
	0	No reaction
17.1	1	Mild and/or transient swelling limited to sensitive area
Edema	2	Moderate swelling persisting over much of the product-exposed area
	3 *	Severe swelling extending over most or all of the product-exposed
0		No reaction
Rash	1	Mild and/or transient rash limited to sensitive area
Rasn	2	Moderate rash persisting over much of the product-exposed area
	3 *	Severe rash extending over most or all of the product-exposed area
0 No reaction 1 Mild and/or tr		No reaction
		Mild and/or transient dryness limited to sensitive area
Dryness	2	Moderate dryness persisting over much of the product-exposed area
	3 *	Severe dryness extending over most of all of the product-exposed area

^{*} A score of 3 in one or more of the conditions evaluated represents significant irritation and qualifies as an Adverse Event.

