14.3.3 Notification

The Sponsor and the reviewing IRB will be notified of all adverse event/experiences that require treatment within 2 business days. Any Serious or Unexpected Adverse Event/Experience that occurs during the study must be reported immediately by the Principal Investigator (or designee) to the Sponsor and the reviewing IRB, followed by written notification within 1 business day of the information being reported to the investigative study team.

Sponsor Notification of Serious Adverse Event:

Primary Contact:	
Telephone:	
Email:	
Secondary Contact:	
Secondary Contact: Telephone:	

The Principal Investigator, [name], and Medical Expert, are required to review all unanticipated problems involving risk to volunteers or others, serious adverse events, and all subject deaths associated with the protocol and provide an unbiased written report of the event. At a minimum, the Principal Investigator and Medical Expert must comment on the outcomes of the event or problem, and in the case of a serious adverse event or death, comment on the relationship to participation in the study.

14.4 **Anticipated Reactions**

The risks associated with this test are primarily related to application of the test materials, and/or the test methodology. Mild abrasion may occur due to cylinder sampling. Folliculitis may be present from clipping. Mild skin irritation is anticipated and in some cases mild to heavy erythema, swelling, itching, cracking, peeling, or in rare cases, blistering and/or an allergic reaction might occur.

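### The only planned between-product irritation test counts any score above zero and gates all further analysis, so a shift from mild (1) to moderate (2) irritation gets no assured comparison

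*Combined protocol and SAP*

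**What the plan says.** Section 7.5 sets the priority: "The principal measures of safety will be skin irritation scores", together with adverse event incidence. It adds that the three products will be compared on irritation, but the method appears only in section 15.4.

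Section 15.4 makes a site's outcome binary. A positive signal is "any reaction above zero (no reaction) on the skin irritation rating scale for any category" (erythema, edema, rash, dryness), and products are compared on it by Fisher's exact test. A further look is conditional on that result, namely on finding "statistically significant skin irritation between the two active treatments and Vehicle Control a secondary analysis will be conducted to determine how the reactions differ". The method of that further look is not given. Section 15.4 also reports the scores of any subject with a 1 or more, and summarizes scores of 3 as adverse events by treatment group.

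Section 14.2 defines the grades. For erythema, 1 is mild and/or transient, while 2 is "Moderate redness persisting over much of the product-exposed area". It states that "Skin irritation scores of 1 or 2 are expected after sampling and product application procedures" and that such scores "are not grounds for dismissal and will not be considered adverse events". Section 14.4 adds "Mild abrasion may occur due to cylinder sampling" and "Mild skin irritation is anticipated and in some cases mild to heavy erythema".

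Section 15.0 defers details to a separate statistical analysis plan, which is not among the documents supplied.

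**The concern.** The comparison codes 1, 2 and 3 alike. Score 3 has its own route through the adverse event tables, but 1 and 2 do not. The one place where grade could be compared is the follow-up analysis, and it depends on a test that cannot see grade.

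The trigger is also worded as the two active treatments against Vehicle Control. It is unclear whether a difference between Investigational Product and Active Control would open it, although that is the best-informed contrast: 48 sites each, with 40 subjects receiving both (section 13.3).

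At stake is what this Phase 2 study can tell the Phase 3 design about tolerability. Sampling abrasion can occur in every arm and may raise above-zero counts for all products. Grade would then carry much of the information that separates them.

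**Working it through.** **Inputs.** Section 13.3 pairs products as 40 (Investigational Product, IP, with Active Control, AC), 8 (IP with Vehicle Control, VC) and 8 (AC with VC). Sites per body area are IP 40 + 8 = 48, AC 40 + 8 = 48 and VC 8 + 8 = 16. The total is 112 sites from 56 subjects, which matches the protocol. The protocol gives no irritation rate or safety power, so every score distribution below is an assumption. Tests are two-sided at 0.05 (section 15.4 states no level), and sites are treated as independent except in the interval check at the end.

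**Step 1: the structural point (no rates needed).** The Fisher table uses only the number of sites with score > 0 and with score 0. Changing a 1 to a 2 alters neither count, so the p-value and the gate are unchanged.

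**Step 2: one worked example, IP vs VC.**
- Score > 0: 45/48 vs 15/16, both 93.75%. Fisher p = 1.00.
- Score ≥ 2: 30/48 (62.5%) vs 2/16 (12.5%). Fisher p = 0.00103.
- Newcombe 95% CI for the score ≥ 2 difference of 0.50. The Wilson limits are 0.484 to 0.748 and 0.035 to 0.360.
  - Lower: 0.50 − √[(0.625 − 0.484)² + (0.360 − 0.125)²] = 0.23
  - Upper: 0.50 + √[(0.748 − 0.625)² + (0.125 − 0.035)²] = 0.65

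Section 15.4 does not say how the Fisher test is laid out. The above-zero result is p = 1.00 under each reading tried: body areas pooled (90/96 vs 30/32), both actives combined against VC (90/96 vs 15/16), and one three-group test (45/48, 45/48, 15/16).

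**Step 3: power under two assumed cases.** Power is the sum over all (x, y) with Fisher p ≤ 0.05 of Bin(x; n₁, p₁) × Bin(y; n₂, p₂).
- Case (a): 85% of comparator sites react; score ≥ 2 on 10% of comparator and 45% of IP sites.
- Case (b): 50% of comparator sites react; score ≥ 2 on 5% of comparator and 30% of IP sites.

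The probit shift at score ≥ 2 is Φ⁻¹(0.45) − Φ⁻¹(0.10) = 1.156 in (a) and Φ⁻¹(0.30) − Φ⁻¹(0.05) = 1.120 in (b). The IP any-reaction rate is then set to rise by none, half or all of that shift: 85%, 94.7% or 98.6% in (a); 50%, 71.2% or 86.9% in (b).

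| Test | IP vs VC (a) | IP vs VC (b) | IP vs AC (a) | IP vs AC (b) |
|---|---|---|---|---|
| Planned (> 0), any-reaction rate unchanged | 2% | 4% | 2% | 3% |
| Planned (> 0), half shift | 20% | 27% | 21% | 48% |
| Planned (> 0), full shift | 40% | 79% | 55% | 97% |
| Fisher at score ≥ 2 | 77% | 50% | 97% | 88% |

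The IP vs AC columns assume that AC scores like VC.

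**Step 4: the proposed interval.** A simulation on the 40/8/8 design used 20,000 trials per case, with latent within-subject correlation 0, 0.3 and 0.6. A Newcombe interval with a covariance term for shared subjects covered 94% to 98%. It excluded zero for IP vs VC in 80–82% of trials in (a) and 58–60% in (b), and for IP vs AC in 98–100% and 93–98%. A subject-clustered Wald interval covered only 90–91% for IP vs VC with 10% of sites at score ≥ 2 in both groups (4,000 trials).

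**The case against.** **The assumed rates are high.** In the cases above, half or more of comparator sites react. The protocol calls such scores expected, which is not a frequency, and subjects scoring 1 before application are dismissed, so sites start at zero. At lower rates with a full shift, the planned test is the better one. With 30% of VC sites reacting and score ≥ 2 at 3% vs 20%, power for IP vs VC is 77% planned against 15% at score ≥ 2. With 20% reacting and 2% vs 10%, it is 48% against 0.2%. This stands, and it is why the above-zero test should stay. It does not help when severity rises alone: the planned test then rejects about 3% of the time at these rates too.

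**The grades are not hidden.** Scores of 1 or more are reported for each affected subject, and copies of the data go into the Final Report (section 17.0). A reader could notice an excess of 2s. That is true, but section 15.4 specifies no summary or comparison by grade and product.

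**The separate analysis plan may cover this.** It may; nothing supplied shows that it does.

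**The denominators are minimum evaluable sites.** Safety uses all randomized subjects, so actual numbers may differ. This affects the illustration, not the structural point.

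**A descriptive table would be enough for an unpowered Phase 2 study.** The table closes much of the gap. An estimated difference with an interval adds little cost and fixes the severity cut-off before unblinding.

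**Conclusion.** The concern holds. As section 15.4 is written, a shift from score 1 to score 2 cannot change the only between-product irritation test or open the analysis that depends on it. That follows from the coding and rests on no assumed rate.

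Its practical size does depend on rates that the protocol does not give. If the any-reaction rate is unchanged, the planned test rejects 2% to 4% of the time in the two main cases, against 50% to 97% for a test at score ≥ 2. If irritation moves fully along one underlying scale, the planned test has 40% to 97% power and is the better test in case (b). Neither cut-point serves both situations, so both are needed. This is a change that should be made, with medium confidence, because materiality depends on unknown rates and the separate analysis plan was not available.

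**What to change.** In section 15.4:

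1. Remove the significance condition on examining how reactions differ.
2. Always tabulate, by product and body area, the maximum post-application score (0 to 3) per treated site, taken over the four categories and the two post-application observations.
3. Compare the proportion of sites scoring 2 or more for IP–VC, AC–VC and IP–AC. Give differences with 95% confidence intervals that allow for subjects who received both products, for example a Newcombe interval with a covariance term.
4. Keep the above-zero Fisher test. State whether it is run by body area, and whether pairwise or as one three-group test.

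An ordinal model could be added as a sensitivity analysis.

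The cost is wording in section 15.4, one table and one further comparison; all scores are already recorded. The downside is one more unpowered safety comparison. With 16 VC sites the intervals are wide: the mean IP–VC width is about 0.32 to 0.50 when 5% to 45% of sites in both groups score 2 or more.
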